9.5.2. Physical Examinations

Physical examinations will be collected during screening, before study drug administration, on day 1 of each treatment cycle and at the Treatment Discontinuation Visit.

A full physical exam will be performed at Screening. Detailed/brief (system-guided) physical examinations will be done at subsequent time points to evaluate any clinically significant abnormalities, including worsening of conditions included in the patient's medical history.

Physical examination results will be listed with vital signs. Changes in weight will be summarized across time on study and the frequency of clinically significant changes will be tabulated overall and by treatment.

9.5.3. Electrocardiograms

Single standard 12 lead digital EKGs will be performed during screening, at Cycle 3 Day 1, Cycle 6 Day 1, Day 1 of every 6th cycle after that, and on the treatment discontinuation visit if not done within the previous 12 weeks.

The EKG (measured after resting in a supine position for 5 minutes) will include heart rate, rhythm, and RR, PR, QRS, QT and QTc intervals. The EKG will be read and interpreted at the investigational site for patient safety monitoring, and documentation stored with the source documents.

Additional correction formulas included but considered secondary are QTcF and QTcB. These additional corrected QT intervals are defined as:

- QTcB is the length of the QT interval corrected for heart rate by Bazett's formula:
 $QTcB = QT / (RR)^{1/2}$
- QTcF is the length of the QT interval corrected for heart rate by Fridericia's formula:
 $QTcF = QT / (RR)^{1/3}$

All EKG parameters and their change from baseline will be summarized across study time points by treatment arm and overall using descriptive statistics. The frequency of abnormal EKG events will be tabulated by treatment arm and overall at each time point.

All EKG values will be listed by patient. Change in EKG findings will also be presented in a separate by-patient listing.

9.5.4. Left Ventricular Ejection Fraction (LVEF)

MUGA scan or ECHO scans to determine LVEF will be performed during screening and repeated at Cycle 3 Day 1, Cycle 6 Day 1, Day 1 of every 6th cycle after that, and at treatment discontinuation, if not done within the previous 12 weeks.

MUGA scans or ECHO scans to determine LVEF will be performed as part of Screening procedures within 2 weeks before Cycle 1/Day 1, unless results are already available from within 4 weeks before Cycle 1/Day 1.

The mean LVEF and mean LVEF change from baseline will be summarized across study time points by treatment arm and overall using descriptive statistics.

All MUGA and ECHO values will be listed by patient. Change in MUGA and ECHO findings will also be presented in a separate by-patient listing.

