^a Since capecitabine is provided as 150 mg or 500 mg tablets, it is recommended that the capecitabine dose reduction(s) is rounded down to the nearest 500 mg or multiple of 150 mg for the BID dose. If the patient's body surface area is >2.0, the standard of care for the study center can be utilized for capecitabine mg/m² dosing.

Left Ventricular Ejection Fraction Toxicity

Guidelines for dose adjustments of **neratinib** in the event of abnormalities in LVEF are shown in Table A2. 5. LVEF assessments will be performed according to the Schedule of Procedures ([Appendix 1](#)). It is strongly recommended to use the same method of cardiac evaluation (ECHO or MUGA) at each time point for each patient.

Table A2. 5 Left Ventricular Ejection Fraction (LVEF) Results Requiring Dose Adjustment of Neratinib

Event on day of scheduled treatment	Actions
Asymptomatic absolute decline of LVEF $\geq 15\%$ from baseline OR absolute decline of LVEF $\geq 10\%$ and below the lower limit of normal of 50%	
A) If LVEF is below 40%: Hold neratinib and seek cardiology input OR continue neratinib with great caution.
 
Initiate monthly monitoring of LVEF
 
 • If while monitoring monthly, LVEF remains $<40\%$: reconsider neratinib only if appropriate and after cardiology consult. • If while monitoring monthly, LVEF increases to $\geq 40\%$: continue neratinib, monitor LVEF every 12 weeks and consider cardiac support with input from cardiologist. 
B) If LVEF is between 40% to 50%: continue neratinib with caution and surveillance.
 
Initiate monthly monitoring of LVEF
 
 • If while monitoring monthly, LVEF falls to $<40\%$: Follow bullet point A instructions described above. • If while monitoring monthly, LVEF remains $\geq 40\%$: continue neratinib, monitor LVEF every 12 weeks and consider cardiac support with input from cardiology.
Symptomatic cardiac failure	
 • Neratinib should be discontinued.

Abbreviations: LVEF: left ventricular ejection fraction

If a patient has a second episode of asymptomatic decline in LVEF that meets either of the above criteria, permanently discontinue **neratinib**, repeat LVEF in 3-4 weeks and consider cardiology consult.

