3. GENERAL ANALYSIS AND REPORTING CONVENTIONS

All study variables will be listed. Selected variables will be summarized and, when appropriate, analyzed. Data summaries will be presented by treatment group and, when appropriate, visit.

For all safety and efficacy variables, the number of patients will be provided overall and by visit, with the exception of adverse events and concomitant medications, which will not be summarized by visit.

Categorical variables will be summarized using counts and percents. Percents will be displayed to 1 place after the decimal point (XX.X), with the exception of 100%, which will be displayed without additional decimal places. Continuous variables will be summarized using number of patients, mean, median, standard deviation, minimum, and maximum.

Mean and median will be reported at 1 more significant digit than the precision of the data; standard deviation will be reported at 2 more significant digits than the precision of the data. Minimum and maximum will be reported to the same level of precision as the original observations. In general, any calculated values, such as those due to unit conversion, will be rounded to the same number of decimal places as the original data. P-values will be reported to 3 decimal places, with values less than 0.001 displayed as '<0.001.'

In general, the baseline value will be considered the last measurement observed prior to taking the first dose of study treatment.

Data will be listed by treatment and patient. In general, listings will be sorted in the order that columns are displayed, starting with the first column on the left (treatment).

SAS statistical software, version 9.1 or later, will be used for all analyses.

If departures from these general conventions are present in the specific evaluations section of this SAP, then those conventions will take precedence over these general conventions.

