12. LIST OF PLANNED TABLES

Grouping	Title
Disposition	Summary of Subject Disposition
	Summary of Protocol Deviations
Demography	Summary of Demographics and Baseline Characteristics
Medical History	Summary of Medical History
Cancer History	Summary of Prior Cancer History and Therapies
	Summary of Baseline Breast Cancer Disease Burden
	Summary of Prior Anticancer Medications
	Summary of Prior Anticancer Radiotherapy
	Summary of Prior Anticancer Surgical Therapy
	Summary of Biomarkers
Concomitant Medications	Summary of Concomitant Medications
	Summary of Non-Pharmacologic Anti-Diarrheal Treatments
Study Medication	Summary of test article exposure
	Summary of test article dose reduction
	Summary of test article dose hold
Efficacy	Summary of Progression-Free Survival
	Summary of Censoring in Progression-Free Survival
	Summary of Objective Response Rate
	Summary of Duration of Response
	Summary of Censoring in Duration of Response
	Summary of Clinical Benefit Rate
	Summary of Overall Survival
Health Outcomes	Summary of Censoring in Overall Survival
	Summary of EORTC QLQ C30 BR23 Observed Results
	Summary of EORTC QLQ C30 BR23 Change from baseline
	Summary of EORTC QLQ C30 BR23 Mixed Model Between Treatment Comparison
	Summary of EQ-5D Observed Results
	Summary of EQ-5D Change from baseline

Grouping	Title
	Summary of EQ-5D Mixed Model Between Treatment Comparison
	Summary of EQ-VAS Observed Results
	Summary of EQ- VAS Change from baseline
	Summary of EQ- VAS Mixed Model Between Treatment Comparison
Safety	Frequency Table of Treatment Emergent Adverse Events by Body System and Preferred Term
	Frequency Table of Serious Adverse Events by Body System and Preferred Term
	Frequency Table of Treatment Emergent Adverse Events Leading to Study Discontinuation by Body System and Preferred Term
	Frequency Table of Treatment Emergent Adverse Events Leading to Study Drug Reduction by Body System and Preferred Term
	Frequency Table of Treatment Emergent Adverse Events Leading to Study Drug Hold by Body System and Preferred Term
	Frequency Table of Treatment Emergent Adverse Events by Body System, Preferred Term and Relationship to Study Medication
	Frequency Table of Treatment Emergent Adverse Events by Body System, Preferred Term and Severity
	Frequency Table of Treatment Emergent Adverse Events by Body System and Preferred Term (Toxicity Grade 3 or Higher)
	Summary of Death
Diarrhea	Summary of Time to First Diarrhea Treatment Emergent Adverse Event

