	Diarrhea Characteristics
	Summary of Time to First Diarrhea Treatment Emergent Adverse Event by Severity
	Summary of Diarrhea Treatment Emergent Adverse Events Leading to Treatment Discontinuation
	Summary of Diarrhea Treatment Emergent Adverse Events Leading to Dose Hold
	Summary of Diarrhea Treatment Emergent Adverse Events Leading to Dose Reduction
	Summary of Anti-diarrheal Medications
Laboratory	Mean and Mean Change from Baseline in Numeric Laboratory Data: Hematology/ Clinical Chemistry/Urinalysis
	Frequency Table of Potentially Clinically Significant Laboratory Data: Hematology/ Clinical Chemistry/Urinalysis

Grouping	Title
	Shift from Baseline in Laboratory Data: Hematology/ Clinical Chemistry/Urinalysis
Vital Signs	Mean and Mean Change from Baseline in of Vital Signs Data
	Frequency Table of Potentially Clinically Significant Vital Signs Data
	Mean and Mean Change from Baseline in ECG Data
Physical Exam	Summary of Physical Examination
ECG	Frequency Table of Potentially Clinically Significant Values in QTc(F) Interval at Post First Dose
	Frequency Table of Potentially Clinically Significant Values in QTc(B) Interval at Post First Dose
	Frequency Table of Potentially Clinically Significant Values in QT Interval at Post First Dose
LVEF	Mean and Mean Change from baseline in LVEF Data

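### The SAP plans no LVEF table that counts patients with a clinically relevant fall; a common-definition count by arm is a minor, cheap addition

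*SAP*

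**What the plan says.** SAP 9.5.4 gives the by-arm LVEF summary in one sentence: "The mean LVEF and mean LVEF change from baseline will be summarized across study time points by treatment arm and overall using descriptive statistics". It adds listings of values and of changes. SAP Section 12 has a single LVEF table, titled "Mean and Mean Change from baseline in LVEF Data", and Section 14 a single LVEF listing. The general convention in SAP Section 3 widens the summary a little: "Continuous variables will be summarized using number of patients, mean, median, standard deviation, minimum, and maximum". SAP Section 13 and the supplemental SAP add nothing on LVEF.

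Other safety measurements get a count of patients. Section 12 lists "Frequency Table of Potentially Clinically Significant Laboratory Data", "Frequency Table of Potentially Clinically Significant Vital Signs Data" and "Frequency Table of Potentially Clinically Significant Values in QTc(F) Interval at Post First Dose", with matching tables for QTcB and QT.

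The protocol's LVEF dose rules differ by arm:
- **Neratinib (Appendix 2, Table A2.5):** the trigger is an asymptomatic absolute fall of at least 15 points, or of at least 10 points to below 50%. If LVEF is then between 40% and 50%, the instruction is to "continue neratinib with caution and surveillance", with monthly scans. Below 40%, the drug may be held or continued with great caution.
- **Lapatinib (Section 6.1.3 and Table A2.12):** the drug is held at Grade 2 or worse, or below the institution's lower limit of normal (50% if none is given). It restarts at a reduced dose only after LVEF has recovered to normal.

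**The concern.** A reader comparing cardiac safety between two HER2-directed regimens needs the number of patients in each arm whose own LVEF fell by a relevant amount, under one definition. The planned LVEF output does not give it. A by-visit mean averages a few large falls with many unchanged values. The minimum shows one patient per visit, not how many crossed a threshold. The listings hold the information, but someone would have to count by hand under a definition chosen after the data are seen.

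The adverse-event tables fill the gap only in part. The one most closely tied to LVEF action, "Frequency Table of Treatment Emergent Adverse Events Leading to Study Drug Hold by Body System and Preferred Term", depends on dose rules that are not the same in the two arms.

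**Working it through.** The plan states no LVEF figure, so there is nothing to reproduce. The check compares the rules and then sizes the dilution and the side effects of the fix.

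**1. Same fall, different action.** Take a fall from 60% to 48% (12 points, below 50%).
- Lapatinib: below the default lower limit and Grade 2 in Table A2.12, so the drug is held.
- Neratinib: the trigger is met, LVEF is between 40% and 50%, so dosing continues with monthly scans.

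Under the minimum rules the drug-hold table can count the first patient and not the second.

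**2. Patients scanned.** Inputs: about 300 per arm (SAP 2.6) and median PFS of 34.7 and 24.3 weeks (Protocol 12.7). Assumption: exponential time on treatment with these medians. The mean is median / ln 2, which is 11.5 and 8.1 months (average 9.8; Protocol 4.1 plans 9.5). Scans fall at Cycles 3, 6 and 12, or weeks 6, 15 and 33. Number on treatment = 300 × 2^(−t/median):

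| Week | Neratinib | Lapatinib |
|---|---|---|
| 6 | 266 | 253 |
| 15 | 222 | 196 |
| 33 | 155 | 117 |

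**3. Dilution.** One 15-point fall moves the neratinib visit mean by 15/266 = 0.06, 15/222 = 0.07 and 15/155 = 0.10 points. For scale, suppose all 300 in an arm are scanned and 3% (9 patients) fall by 15 points. The mean moves by 0.03 × 15 = 0.45. The standard error of the between-arm difference is SD × √(2/300), which is 0.41 to 0.57 for an assumed SD of change of 5 to 7. Nine such patients would barely show.

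**4. Patients with no post-dose scan.** The screening scan may be 28 days before randomization (Protocol 8.2.5), dosing may start 14 days after randomization (4.2.2), and Cycle 3 Day 1 is 42 days after the first dose: 28 + 14 + 42 = 84 days, or 12 weeks. A discontinuation scan is needed only if none was done in the previous 12 weeks (Appendix 1, footnote h). A patient who stops before Cycle 3 Day 1 therefore need not have one: 300 − 266 = 34 neratinib and 300 − 253 = 47 lapatinib patients (11% and 16%).

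**5. Bias of a worst-value count.** Among patients with at least one scan, expected scans are 1 + A + A × (2^(−12/m) − 2^(−18/m)), where m is the median and A = 2^(−9/m) / (1 − 2^(−18/m)). The last term is the discontinuation scan.
- Neratinib: A = 0.835/0.302 = 2.77, giving 1 + 2.77 + 2.77 × 0.089 = 4.0.
- Lapatinib: A = 0.774/0.402 = 1.93, giving 1 + 1.93 + 1.93 × 0.112 = 3.1.

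Assume no drug effect and independent scans. The chance p of a 15-point fall per scan is Φ(−15/6) = 0.62% for an SD of 6 and Φ(−15/8) = 3.04% for an SD of 8. Averaging 1 − (1 − p)^k over the number of scans k gives about 2.5% versus 1.9% (SD 6) and 11% versus 9% (SD 8), neratinib versus lapatinib. Through Cycle 6 Day 1 there are one or two scans, the second with probability 0.835 or 0.774. The chance is p + q × p × (1 − p), where q is that probability: 1.1% versus 1.1% (SD 6) and 5.5% versus 5.3% (SD 8). Independence overstates the gap, because all changes share one baseline scan. These figures cover the 15-point threshold only.

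**6. Unscheduled scans.** A neratinib patient at 48% from 60% starts monthly scans. A later 44% is a 16-point fall and newly meets the 15-point threshold. A lapatinib patient at 48% from 55% is held with a 7-point fall. A rescan before restart at 44% is an 11-point fall to below 50% and newly meets the 10-point threshold. Arm-specific follow-up can therefore raise any count.

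**The case against.** The strongest reply is that nothing is lost. All values and changes are listed by patient, the minimum and maximum appear by visit, and an independent committee reviews safety throughout (SAP 10). The TEAE tables by preferred term, by severity and for Grade 3 or higher do not depend on a dose hold. Protocol 13.1.1 treats any unfavourable and unintended sign as an adverse event. Section 13.1.2, though headed laboratory results, includes findings that need further diagnostic testing or that the investigator judges to be an event. A neratinib fall to 48% can therefore be counted there, and the missing count could be produced later without touching any hypothesis test.

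Most of this stands, and it sets the weight of the point. A reader might infer that LVEF falls would go uncounted by arm altogether. The documents do not support that: coverage is partial, and under-reporting is possible but not stated. Nor will the drug-hold table necessarily omit every neratinib patient, since Section 6.1.3 calls the dose rules a minimum and lets investigators do more.

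What does not stand is that the listings and extremes are enough. The minimum identifies one patient per visit, and a hand count leaves the definition open until after the data are seen. The SAP itself treats listings as insufficient for laboratory, vital-sign and QT/QTc data.

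A second objection is that worst-value counts work against the arm treated longer. That is correct. The gap is modest and almost disappears through Cycle 6 Day 1.

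**Conclusion.** The gap is real and minor. LVEF is summarised by arm only as by-visit continuous statistics plus listings. The TEAE tables count some falls, depending on investigator reporting in an open-label trial. The drug-hold table is not comparable between arms because the LVEF dose rules differ.

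A reader might also infer that the plan hides a cardiac excess on neratinib. The documents give no LVEF-decline rate for either regimen, and Protocol 2.2.3.3 reports no neratinib-related Grade 3 or 4 cardiotoxicity in the earlier phase 2 single-agent study. No excess is claimed here, and neither the co-primary endpoints nor the alpha allocation is affected.

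The reading of the SAP rests on its text alone. The sizes rest on 300 per arm, exponential time on treatment at the planned PFS medians, and assumed SDs of LVEF change (5 to 8 points) that the documents do not supply.

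**What to change.** Add to SAP 9.5.4 and Section 12 one descriptive table by arm of worst post-first-dose LVEF, with identical definitions in both arms. Show n and % with:
- (a) an absolute fall of 10 points or more to below 50%;
- (b) an absolute fall of 15 points or more;
- (a) or (b);
- (c) LVEF below 50% or below the institution's lower limit of normal, which covers the lapatinib trigger. At a site with a limit of 55%, a fall from 58% to 54% requires a hold but meets neither (a) nor (b);
- (d) LVEF below 40%, which is a subset of (a) for anyone eligible at entry (LVEF at least 50%);
- worst CTCAE grade as a count. A shift table would be nearly empty, because almost every patient starts ungraded.

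Base the main version on scheduled and treatment-discontinuation scans, overall and through Cycle 6 Day 1. Use patients with at least one post-first-dose LVEF as the denominator, and report by arm the number without one and the number of scans per patient. If a version with unscheduled scans is also shown, label it as affected by arm-specific follow-up (monthly scans on neratinib, rescans before restart on lapatinib), which can raise any row.

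Cost: SAP wording and one table from data already collected, with no new scans. Downside: worst-value counts rise modestly with longer time on treatment, which is why the Cycle 6 column and the scans per patient are needed.

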9.5.5. Liver Function Test Results

A listing will be generated for patients potentially meeting Hy's Law criteria (total bilirubin \geq (2xULN) and AST or ALT $>$ (3xULN) at any time during the study). Plots or tables of on-therapy peak total bilirubin vs. peak AST (or ALT) will also be generated to help identify potential Hy's Law cases.

9.5.6. ECOG Performance Status

ECOG performance status will be assessed at screening, Day 1 of every cycle, and at treatment discontinuation in accordance with the Schedule of Procedures in the study protocol. The ECOG categories are also summarized in the study protocol.

Screening ECOG performance status may be accepted as the Baseline status if the assessment was performed within 72 hours of initiation of investigational product and there are no clinically significant findings.

The ECOG status will be included in the baseline and demographic variables. The number and percentages of patients in each ECOG category will be presented by treatment and overall.

10. INTERIM ANALYSES AND DATA MONITORING

No interim PFS analysis is planned. One OS interim analysis is planned at the time of the primary PFS analysis. An Independent Data Monitoring Committee will review safety data on an ongoing basis throughout the study.

11. CHANGES TO THE ANALYSES PLANNED IN THE PROTOCOL

This section is to be filled out if there are any changes to the analyses prior to finalization of the SAP.

12. LIST OF PLANNED TABLES

Grouping	Title
Disposition	Summary of Subject Disposition
	Summary of Protocol Deviations
Demography	Summary of Demographics and Baseline Characteristics
Medical History	Summary of Medical History
Cancer History	Summary of Prior Cancer History and Therapies
	Summary of Baseline Breast Cancer Disease Burden
	Summary of Prior Anticancer Medications
	Summary of Prior Anticancer Radiotherapy
	Summary of Prior Anticancer Surgical Therapy
	Summary of Biomarkers
Concomitant Medications	Summary of Concomitant Medications
	Summary of Non-Pharmacologic Anti-Diarrheal Treatments
Study Medication	Summary of test article exposure
	Summary of test article dose reduction
	Summary of test article dose hold
Efficacy	Summary of Progression-Free Survival
	Summary of Censoring in Progression-Free Survival
	Summary of Objective Response Rate
	Summary of Duration of Response
	Summary of Censoring in Duration of Response
	Summary of Clinical Benefit Rate
	Summary of Overall Survival
Health Outcomes	Summary of Censoring in Overall Survival
	Summary of EORTC QLQ C30 BR23 Observed Results
	Summary of EORTC QLQ C30 BR23 Change from baseline
	Summary of EORTC QLQ C30 BR23 Mixed Model Between Treatment Comparison
	Summary of EQ-5D Observed Results
	Summary of EQ-5D Change from baseline

Grouping	Title
	Summary of EQ-5D Mixed Model Between Treatment Comparison
	Summary of EQ-VAS Observed Results
	Summary of EQ- VAS Change from baseline
	Summary of EQ- VAS Mixed Model Between Treatment Comparison
Safety	Frequency Table of Treatment Emergent Adverse Events by Body System and Preferred Term
	Frequency Table of Serious Adverse Events by Body System and Preferred Term
	Frequency Table of Treatment Emergent Adverse Events Leading to Study Discontinuation by Body System and Preferred Term
	Frequency Table of Treatment Emergent Adverse Events Leading to Study Drug Reduction by Body System and Preferred Term
	Frequency Table of Treatment Emergent Adverse Events Leading to Study Drug Hold by Body System and Preferred Term
	Frequency Table of Treatment Emergent Adverse Events by Body System, Preferred Term and Relationship to Study Medication
	Frequency Table of Treatment Emergent Adverse Events by Body System, Preferred Term and Severity
	Frequency Table of Treatment Emergent Adverse Events by Body System and Preferred Term (Toxicity Grade 3 or Higher)
	Summary of Death
Diarrhea	Summary of Time to First Diarrhea Treatment Emergent Adverse Event
	Diarrhea Characteristics
	Summary of Time to First Diarrhea Treatment Emergent Adverse Event by Severity
	Summary of Diarrhea Treatment Emergent Adverse Events Leading to Treatment Discontinuation
	Summary of Diarrhea Treatment Emergent Adverse Events Leading to Dose Hold
	Summary of Diarrhea Treatment Emergent Adverse Events Leading to Dose Reduction
	Summary of Anti-diarrheal Medications
Laboratory	Mean and Mean Change from Baseline in Numeric Laboratory Data: Hematology/ Clinical Chemistry/Urinalysis
	Frequency Table of Potentially Clinically Significant Laboratory Data: Hematology/ Clinical Chemistry/Urinalysis

Grouping	Title
	Shift from Baseline in Laboratory Data: Hematology/ Clinical Chemistry/Urinalysis
Vital Signs	Mean and Mean Change from Baseline in of Vital Signs Data
	Frequency Table of Potentially Clinically Significant Vital Signs Data
	Mean and Mean Change from Baseline in ECG Data
Physical Exam	Summary of Physical Examination
ECG	Frequency Table of Potentially Clinically Significant Values in QTc(F) Interval at Post First Dose
	Frequency Table of Potentially Clinically Significant Values in QTc(B) Interval at Post First Dose
	Frequency Table of Potentially Clinically Significant Values in QT Interval at Post First Dose
LVEF	Mean and Mean Change from baseline in LVEF Data

